Appendix F Data Handling Rules

Appendix G Programming Codes for Statistical Analysis

1. BACKGROUND

Stroke is the fourth leading cause of death and a leading cause of disability in the United States (U.S.). More than half of all ischemic stroke patients have mild strokes at initial presentation in population-based studies (3; 10). Alteplase is the only approved therapeutic agent for the treatment of AIS (acute ischemic stroke) and is widely accepted as the standard of care for eligible patients (4; 6). The currently approved Activase® (alteplase) U.S. Package Insert (USPI) contains wording that recommends against use of alteplase in patients with “minor neurological deficit or with rapidly improving stroke symptoms” due to the fact this patient population has not been evaluated. Furthermore, the current American Heart Association/American Stroke Association Council Guidelines include “minor and rapidly improving stroke symptoms (clearing spontaneously)” as a relative exclusion criterion for alteplase (6). This is largely due to the aforementioned label wording not recommending treatment of patients with minor neurological deficit or with rapidly improving stroke symptoms (RISS), the lack of a consistent and consensus definition of who constitutes this patient population, and the absence of definitive evidence of alteplase efficacy in this setting (TREAT Task Force 2013). Therefore, this trial is designed to evaluate the efficacy and safety of alteplase in confirmed AIS patients with minor neurological deficit or with RISS, which will be referred to collectively as “mild stroke”.

For further background information see Section 1 of the protocol.

The original plan was for approximately 948 patients with mild stroke to be enrolled and randomized in a 1:1 ratio to two treatment groups. However the study enrollment was prematurely terminated due to recruitment below target in December 2016 (at approximately 1/3 of original planned enrollment of 948) and the analysis will be performed using available data from patients randomized prior to study termination.

This Statistical Analysis Plan (SAP) describes the statistical methods to be used for the clinical study report of study ML29093. This version of the SAP has been developed using version 3 of the study protocol dated 08 Jan 2015. The SAP will be finalized by [REDACTED] and approved by Genentech, Inc. before database lock and unblinding.

Statistical Analysis Plan: Alteplase—Genentech USMA

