2.3 DETERMINATION OF SAMPLE SIZE

The sample size was originally determined as follows.

A sample size of 856 is required in order to achieve 80% power in the primary analysis to detect effect size of 9% absolute difference in the proportion of patients with favorable outcomes [mRS of 0 or 1 at Day 90] between the alteplase and control arms. The above power consideration assumes a control proportion of 65% and Type I error of 0.025 (one-sided), and uses a group sequential design with one interim analysis for futility (non-binding), based on O'Brien and Fleming boundary, conducted after 50% of the anticipated sample size have completed 90-day follow-up assessments. [REDACTED] was used in sample size calculation.

The intention-to-treat principle will be applied to the primary analysis and, therefore, to safeguard against dilution of the treatment effect associated with an approximate 5% non adherence rate (due to loss to follow-up, consent withdrawal, treatment crossovers and stroke mimics), the above sample size was inflated by a factor of 1.108 (5). Therefore, a total sample size of 948 was planned for this study.

The study enrollment was terminated early in December 2016, after 313 patients were randomized. The analysis will be carried out based on all available data from patients randomized prior to termination. With this sample size, power calculations show that the study will be substantially underpowered to conduct superiority tests (Table 1). Therefore, all efficacy analyses will include estimation of treatment effects with the associated two-sided 95% confidence intervals.

Table 1			
Estimated Power for the Final Sample Size (N=313)			
Assumed Effect Size	7%	8%	9%
Statistical Power ^a	25%	31%	38%
^a Based on the t-test for the observed proportions of mRS 0-1 at Day 90, using type I error of 0.025, one-sided. Assumptions are based on a blinded evaluation of non-adherences in the Jan 2017 Development Safety Update Report (DSUR) dataset: - Control response rate among confirmed strokes is 74%. - 10% of randomized subjects are stroke mimics and 80% of those stroke mimics will have favorable outcome. - 1% of subjects received concomitant tPA - 7.4% subjects without Day 90 outcome (290 effective sample size)			

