4.4.1 Primary Efficacy Endpoint

The primary efficacy analysis will estimate the effect of treatment with IV alteplase therapy and with the standard medical care (aspirin) in AIS patients with mild symptoms. The primary efficacy outcome is derived from the mRS.

The mRS is an assessment of disability with values from 0 (no symptoms at all) to 5 (severe disability); death will be scored as a '6'. The mRS is collected at 30 and 90 days after start of study drug administration. If death occurs prior to an assessment day (Day 30 or Day 90), the mRS will be considered available and will be set to 6.

The proportion of patients within each treatment group with a favorable outcome, defined by mRS of 0 or 1 at 90 days post-randomization, will be estimated in the IV alteplase arm and in the standard medical care arm. Reasons for not performing the assessment of mRS at Day 90 will be summarized.

The difference in proportions between the two groups will be estimated using the risk difference. The risk difference will be obtained from a linear model with the binary mRS 0-1 outcome as the response, treatment, and age, time from last known well to treatment, and baseline NIHSS as continuous covariates. Quadratic terms for the continuous covariates may be added to the model, if the Wald p-value for the quadratic term is <0.1. No interactions among the covariates will be included in this model.

A common approach for implementation of this model is binary regression, a GLM with the Bernoulli distribution for the outcome and the identity link function. This

Statistical Analysis Plan: Alteplase—Genentech USMA
14/ML29093 5/17/2017

model has a possibility of non-convergence when the estimated response probability falls outside of the (0,1) interval. To circumvent the non-convergence problem, an approach of using the ordinary least squares with a robust standard error is used in this study. It was shown that if a robust standard error is used with the ordinary least squares estimation, the estimate of the risk difference is equal or similar to the estimate from the GLM with an identity link for Bernoulli outcome approach (22, 23).

The primary efficacy analysis will include all ITT patients, with patients grouped according to the treatment assigned at randomization. Missing or out of window mRS at Day 90 will be imputed with LOCF or late Day 90 mRS, if available, or simulated with a hot deck method (see Section 4.7 for handling of missing mRS).

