4.7 HANDLING OF DROPOUTS, MISSING/INCOMPLETE DATA, OR OUTLIERS

For the analyses of the mRS based endpoints, last observation carried forward will be used to impute missing or out of window assessments of mRS at Day 90. The mRS result carried forward needs to be on or after Day 4 to qualify for this imputation. If there is no in-window or LOCF assessment of mRS, then a late Day 90 mRS will be used if available.

ITT patients without any observed mRS past day 4 will have their Day 90 mRS simulated by a hot deck method. This will be an adjustment cells imputation (24), with the cells defined by treatment group, age (< 65 vs. ≥ 65), pre-treatment NIHSS score (0 – 2 vs. 3 – 5), and last known well time to treatment (0 – 2 hours vs. > 2 hours). For each patient with a missing mRS score, a “donor” patient will be drawn at random from the pool of patients with available mRS and who belong to the same cell as the recipient (i.e. randomized to the same treatment group and having the

Statistical Analysis Plan: Alteplase—Genentech USMA
30/ML29093 5/17/2017

same categories for age, last known well time to treatment and baseline NIHSS). The imputed mRS will then be the mRS value of the “donor”.

It is expected that only a small number of patients will need the hot deck imputation; therefore, the techniques recommended in (24) for a variance estimate that incorporates the additional variance from the missing information will not be implemented.

No imputation of missing patient reported outcomes, cognitive assessments, or the 10-meter walk test will be performed except as specified in the scoring rules for the assessment. Reasons for the assessment not being performed will be summarized by the number and percentage in each category by treatment group.

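### Section 4.7 analyses one random hot-deck draw as observed data, so the primary CI is slightly too narrow, and it lets a Day 30 score outrank a nearer late Day 90 score

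*SAP*

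**What the plan says.** Section 4.7 orders the handling of a Day 90 mRS that is missing or outside the analysis window. LOCF comes first, from any mRS on or after Day 4. Then: "If there is no in-window or LOCF assessment of mRS, then a late Day 90 mRS will be used if available". Patients still without a value receive the mRS of one donor, drawn at random from the same cell of treatment, age, baseline NIHSS and time to treatment. The SAP expects few such patients and concludes: "therefore, the techniques recommended in (24) for a variance estimate that incorporates the additional variance from the missing information will not be implemented". It gives no expected number, and no threshold above which the shortcut would be abandoned.

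Section 4.4.1 applies this to the primary endpoint: "Missing or out of window mRS at Day 90 will be imputed with LOCF or late Day 90 mRS", with the hot deck for the rest. The primary model is a linear regression on the completed ITT set, and Appendix G codes it with an HC0 robust standard error. Section 4.4 refers to Appendix D for more detail on mRS imputation, but Appendix D contains none, so no seed is fixed.

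The only figure on missingness is in the notes to Table 1 in Section 2.3: "7.4% subjects without Day 90 outcome (290 effective sample size").

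**The concern.** Since enrolment stopped, the SAP confines efficacy to estimates with 95% intervals (Sections 2.3 and 4.4), so the interval is the main result.

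The first issue is variance. A single donor value carries no new information about the patient who lacks an outcome, yet the regression counts that row as a full observation. The draw itself also adds noise that the robust standard error cannot see. Both effects make the reported interval too short, and the point estimate depends on an unspecified random draw. Table 1 credits the trial with 290 informative patients, whereas the primary interval treats all 313 as informative.

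The second issue is order. Section 4.4.1 and the schedule in Appendix B have mRS collected only at Days 30 and 90, so LOCF will normally be the Day 30 telephone score. Ranking it above an observed late score can discard the measurement nearer to the target day.

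The same completed mRS values feed the ordinal, global, mRS 0 and logistic analyses. The only mRS 0-1 analysis without imputation is an exploratory GEE odds ratio, so no planned risk difference would show how sensitive the result is to these rules.

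**Working it through.** **Inputs.** From Section 2.3: N = 313 ("after 313 patients were randomized"), 290 effective, control response 74% in confirmed strokes, 10% mimics with 80% favorable, 1% concomitant tPA, effects of 7, 8 and 9 points, "using type I error of 0.025, one-sided". From Section 1: allocation "enrolled and randomized in a 1:1 ratio to two treatment groups", so about 156.5 per arm. The hot-deck count is not given, so I varied it over 3, 6, 12 and 23. The last is 313 − 290 = 23, or 7.4% of 313.

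**Reproducing Table 1.** With 145 per arm, the control rate is 0.9 × (0.74 + 0.01d) + 0.1 × 0.80 and the alteplase rate is 0.9 × (0.74 + d) + 0.1 × 0.80. For d = 0.09 these are 0.7468 and 0.827. A normal approximation with pooled variance under the null gives power of 24.7%, 31.2% and 38.4% for d = 7, 8 and 9 points, against 25%, 31% and 38% in the SAP. The inputs are therefore read correctly, and Table 1 does rest on 290 patients.

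**Variance of a single draw.** Take n per arm, r with an observed value and m = n − r hot-decked, missing completely at random and split equally between arms:

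true variance / reported variance = n/r + (m/n)(1 − 1/r)

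The first term is the lost information and the second is the noise of the draw. For the half-width I used the unadjusted risk difference at 74.6% vs 82.7% (the 9-point effect diluted by mimics, ignoring the 1% tPA). The reported SE is √[(0.746 × 0.254 + 0.827 × 0.173)/156.5] = 0.0461, so the reported half-width is 1.96 × 0.0461 = 9.04 points. Coverage is 2Φ(1.96 / SE ratio) − 1.

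| Hot-decked, both arms | r per arm | n/r | (m/n)(1 − 1/r) | Variance ratio | SE ratio | Coverage | True half-width (points) |
|---|---|---|---|---|---|---|---|
| 3 | 155 | 1.0097 | 0.0095 | 1.0192 | 1.010 | 94.8% | 9.12 |
| 6 | 153.5 | 1.0195 | 0.0190 | 1.0386 | 1.019 | 94.6% | 9.21 |
| 12 | 150.5 | 1.0399 | 0.0381 | 1.0780 | 1.038 | 94.1% | 9.38 |
| 23 (ceiling) | 145 | 1.0793 | 0.0730 | 1.1523 | 1.073 | 93.2% | 9.70 |

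The draw alone has an SD of 0.45 points on the risk difference with 3 patients and 1.25 points with 23. This is already inside the ratios above and must not be added to them.

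**Simulation check.** I ran 20,000 trials with eight equal cells per arm, data missing completely at random and the unadjusted risk difference. Coverage was 94.7% with none missing, 94.3% with 6, 93.7% with 12 and 93.2% with 23. The ratio of actual to reported SE was 1.013, 1.027, 1.046 and 1.071. The Monte Carlo error of coverage is about 0.17 points. Since the no-missing baseline is itself 94.7%, the loss due to the hot deck at the ceiling is about 1.5 points.

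**Order of the rules.** Section 4.4 adopts a 30-day analysis window. Read as plus or minus 30 days, it accepts Days 60 to 120, so a late score means Day 121 or after. A Day 30 score lies 60 days from Day 90. A Day 121 score lies 31 days away and a Day 149 score 59 days away. From Day 121 to Day 149, then, the rule discards the nearer observation.

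**The case against.** The shortcut is disclosed and given a reason. The 7.4% counts patients without a Day 90 outcome, not hot-deck patients: LOCF and late scores are used first, and a death before Day 90 is scored 6 and counts as available. If only 3 to 6 patients remain, the SE is understated by 1% to 2% and the half-width moves from 9.04 to 9.12 or 9.21 points. No superiority decision depends on the interval, and nothing read from an interval of this width would plausibly change. All of this stands and limits the size of the point. It does not make the interval correct, and the SAP sets no limit at which its expectation of few patients would be revisited.

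On the order of the rules, a reader might infer that some primary outcomes will be wrong. The SAP does not support that. It gives no count of patients with both a Day 30 and a late Day 90 score, and no rate of change in mRS 0-1 between them. The widened window should make late scores uncommon, and a late score is not a Day 90 score either. One changed outcome would move an arm by 1/156.5 = 0.64 points, but that describes a single hypothetical patient, not an effect in this trial.

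A reader might also infer that LOCF should give way to full multiple imputation of every missing score. The defect lies in the position of LOCF and in the omitted variance; removing LOCF altogether would be a preference.

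**Conclusion.** The point holds at modest size. As written, the primary 95% CI is too narrow if any patient is hot-decked. The SE is understated by about 1% to 2% with 3 to 6 patients, about 4% with 12, and about 7% at the ceiling of 23, where coverage is about 93.2%. These figures assume data missing completely at random, an equal split between arms, and the unadjusted risk difference as a stand-in for the covariate-adjusted one.

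Independently, the order of the rules can replace an observed score with one further from Day 90, for late scores from about Day 121 to Day 149. That range rests on the plus or minus reading of the 30-day window and on a carried-forward score taken at Day 30. The number affected is unknown, so no bias is shown. Both matters should be fixed because they touch the primary estimate and are cheap to correct, but neither overturns the analysis.

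**What to change.** In Section 4.7, with matching changes in Section 4.4.1 and Table 2:

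1. Use the in-window mRS, then an observed late Day 90 mRS, then LOCF, then the hot deck.
2. Repeat the hot-deck draw with a fixed seed, for example 50 sets, and combine by Rubin's rules (reference 11 is already listed). The draw should reflect uncertainty in the donor pool, for instance through an approximate Bayesian bootstrap within cells. Alternatively, keep one draw and apply the variance estimate from reference 24.
3. Report the number of patients imputed under each rule, by arm, and keep the current rule as a sensitivity analysis of the risk difference.

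The cost is SAP wording and minor programming on data already collected. The primary CI becomes at most about 7% wider (9.70 against 9.04 points, for a corrected single draw at the ceiling). Repeated draws average out the noise of the draw, so the half-width at the ceiling would be nearer 9.04 × √1.0793 = 9.39 points, about 4% wider.

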4.8 INTERIM ANALYSES AND/OR SAFETY REVIEWS

One interim analysis of the primary efficacy outcome was planned for clear futility after approximately 50% of patients have completed or discontinued from the study, but this analysis was not performed due to early termination of the study. In addition, there were 4 planned safety reviews, of which two have occurred after 5% (50), and 25% (237) of patients have been enrolled.

Details on the procedures for the safety reviews and the interim analysis are in the Charter for the iDMC.

Statistical Analysis Plan: Alteplase—Genentech USMA
33/ML29093 5/17/2017

Appendix A Protocol Synopsis

PROTOCOL SYNOPSIS

TITLE: A PHASE IIIB, DOUBLE-BLIND, MULTICENTER STUDY TO EVALUATE THE EFFICACY AND SAFETY OF ALTEPLASE IN PATIENTS WITH MILD STROKE (RAPIDLY IMPROVING SYMPTOMS AND MINOR NEUROLOGIC DEFICITS [PRISMS])

PROTOCOL NUMBER: ML29093

VERSION NUMBER: 3

EUDRACT NUMBER: N/A

IND NUMBER: 3811

TEST PRODUCT: Alteplase (RO5532960)

PHASE: IIIb

INDICATION: Acute ischemic stroke

SPONSOR: Genentech, Inc.

DATE FINAL: Version 1: 27 November 2013

DATE AMENDED: Version 2: 22 August 2014
Version 3: 17 December 2014

Objectives

Primary Objectives

The primary objective of this study is to determine the efficacy of intravenous (IV) alteplase for treatment of acute ischemic stroke (AIS) in patients with mild stroke (also known as “minor neurologic deficit” and “rapidly improving stroke symptoms”), defined as a National Institutes of Health Stroke Scale (NIHSS) score ≤ 5 and not clearly disabling, within 3 hours of last known well time as measured by the proportion of patients with a modified Rankin Scale (mRS) score of 0–1 at Day 90.

Secondary Objectives

The secondary objectives of this study are as follows:

To further evaluate efficacy of IV alteplase to improve mild stroke outcomes at Day 90 via:

Ordinal mRS

Global favorable recovery (Global Outcome Measure derived from mRS 0-1, NIHSS 0-1, Barthel Index [BI] ≥ 95 , and Glasgow Outcome Scale [GOS] = 1)

To evaluate safety as measured by:

Symptomatic intracranial hemorrhage (sICH) within 36 hours – primary safety assessment

Any intracranial hemorrhage (ICH) within 36 hours

Mortality within 90 days

Statistical Analysis Plan: Alteplase—Genentech USMA
34/ML29093 5/17/2017

Stroke-related and neurological deaths within 90 days
Incidence, severity, and spectrum of all adverse events (AEs) and serious adverse events (SAEs)

Exploratory Objectives

The exploratory objectives for this study include subgroup analyses of the primary efficacy outcome variable in subgroups defined by age (< 65 vs. ≥ 65), pre-treatment NIHSS score (0 – 2 vs. 3 – 5), last known well time to treatment (0 – 2 hours vs. > 2– 3 hours), and stroke subgroups (rapidly improving stroke symptoms [RISS] vs. non-RISS), respectively.

The following endpoints will also be explored:

NIHSS

BI

GOS

Stroke recurrence (based on AE monitoring) within 90 days

Cognition and behavior (modified 30-minute battery: Controlled Oral Word Association test; Hopkins Verbal Learning Test-Revised [HVLTR] trials 1, 2, and 3; digit symbol coding from the Wechsler Adult Intelligence Scale III [WAIS III]; Forward and Backward Digit Span test; Benton Judgment of Line Orientation, form V; HVLTR trial 4 and recognition; semantic fluency [Animal Naming test]; and Boston Naming Test [BNT; 15-item short form]) at Day 90

Ambulatory performance (as measured by walking speed) at Day 90

Center for Epidemiologic Studies-Depression (CES-D)

Quality of life (European Quality of Life [EQ-5D] questionnaire) at Day 90

Stroke Impact Scale-16 (SIS-16) at Day 90

Study Design

Description of Study

PRISMS is a double-blind, multicenter, randomized, Phase IIIb study to evaluate the efficacy and safety of IV alteplase in AIS patients with mild strokes that do not appear to be clearly disabling. The trial will consist of a screening assessment, randomization, and treatment followed by a *Day 5 visit*, 30-day phone call, and a 90-day follow-up visit. Treatment should start within 3 hours from last known well time (stroke symptom onset).

Screening assessments will be used to determine the eligibility of the patient. Patients meeting eligibility criteria will be randomized in a 1:1 ratio to receive either:

1. One dose of alteplase 0.9 mg/kg IV (not to exceed 90 mg) and one dose of oral aspirin placebo, OR
2. One dose of IV alteplase placebo and one dose of oral aspirin 325 mg.

Number of Patients

Approximately 948 patients with AIS and mild strokes will be enrolled in the study across 75 sites in North America.

Target Population

Inclusion Criteria

Patients must meet the following criteria for study entry:

Age ≥ 18 years (no upper age limit)

Mild ischemic stroke defined as the most recent pre-treatment NIHSS score of ≤ 5 and determined as not clearly disabling by the investigator. This includes patients with persistently mild deficits as well as those who improve to a pre-treatment NIHSS score ≤ 5 (also known as RISS).

Study treatment can be initiated within 3 hours of last known well time without stroke symptoms (i.e., last seen normal).

Statistical Analysis Plan: Alteplase—Genentech USMA

35/ML29093

5/17/2017

Signed informed consent prior to initiation of any study-specific procedure or treatment. The patient or the patient's legally authorized representative must be able to provide written informed consent and understand the potential risks and benefits from study enrollment and treatment.

Exclusion Criteria

Patients who meet any of the following criteria will be excluded from study entry:

Computed tomography (CT) or magnetic resonance imaging (MRI) findings consisting of one of the following:

- CT with clear large hypodensity that is greater than one-third middle cerebral artery (MCA) territory (or greater than 100 cc if not in MCA territory),
- MRI with clear large hyperintensity on concurrent diffusion-weighted (DW) and fluid-attenuated inversion recovery (FLAIR) that is greater than one-third MCA territory (or greater than 100 cc if not in MCA territory),
- Imaging lesion consistent with acute hemorrhage of any degree, OR
- Evidence of intraparenchymal tumor

Disability prior to the presenting stroke (historical mRS score ≥ 2)

Standard contraindications to IV alteplase for patients treated within 3 hours of symptom onset, including:

- Head trauma or previous stroke within the previous 3 months
- Myocardial infarction within the previous 3 months
- Gastrointestinal or urinary tract hemorrhage within the previous 21 days
- Major surgery within the previous 14 days
- Arterial puncture at a non-compressible site within the previous 7 days
- Any history of ICH with the exception of < 5 chronic microbleeds on MRI
- Elevated blood pressure (systolic > 185 mm Hg or diastolic > 110 mm Hg), or the use of aggressive measures (use of more than two intravenous agents to lower blood pressure) to achieve blood pressure within acceptable parameters
- Treatment with unfractionated heparin within the last 48 hours and activated partial thromboplastin time outside of the normal range as specified by the center's local laboratory
- Blood glucose < 50 mg/dL
- International normalized ratio > 1.7 (Note: This does not need to be verified prior to randomization if there is no clinical suspicion of abnormality.)
- Platelet count of $< 100,000/\text{mm}^3$ (Note: This does not need to be verified prior to randomization if there is no clinical suspicion of abnormality.)
- Treatment with a direct thrombin inhibitor or factor Xa inhibitor (including novel oral anticoagulants [e.g., dabigatran, rivaroxaban, apixaban, edoxaban]) within the last 48 hours
- Treatment with a low-molecular-weight heparin (e.g., dalteparin, enoxaparin) within the last 48 hours

Allergic reactions to study drug or aspirin, or nonsteroidal anti-inflammatory drugs (NSAIDs)

Females of childbearing age who are known to be pregnant and/or lactating, or who have a positive pregnancy test on admission

Inability to swallow, which would prevent oral intake of aspirin or aspirin placebo tablet

Other serious, advanced, or terminal illness that would confound the clinical outcome at 90 days

Current or recent (within 3 months) participation in another investigational drug treatment protocol

Anticipated inability to obtain 3-month follow-up assessments

Previous enrollment in PRISMS

Any other condition that the investigator feels would pose a significant hazard to the patient if treatment with alteplase is initiated

Statistical Analysis Plan: Alteplase—Genentech USMA
36/ML29093 5/17/2017

Length of Study

Based on study enrollment projections, this study is estimated to take approximately 4 years to complete, from first patient in to last patient's last visit (LPLV), when the final patient completes the 90-day follow-up.

End of Study

The end of the study is defined as the date when the LPLV occurs. The LPLV is expected to occur approximately 90 days (± 14 days) after the last patient is enrolled into the study.

Efficacy Outcome Measures

The primary efficacy outcome measure for this study is:

A favorable functional outcome, defined by an mRS score of 0 or 1 at Day 90 post-randomization

All mRS assessments will be made by investigators blinded to treatment assignment who are trained and certified in mRS administration

The secondary efficacy outcomes at Day 90 include:

Ordinal mRS

Global favorable recovery (Global Outcome Measure derived from mRS 0-1, NIHSS 0-1, BI ≥ 95 , and GOS 1)

Safety Outcome Measures

The safety outcome measures for this study are as follows:

Incidence of sICH within 36 hours (primary safety assessment)

sICH is defined as any neurological decline attributed to new ICH seen on imaging by the investigator. New ICH seen on imaging will be later confirmed on independent reading by blinded central study radiologists.

Any ICH within 36 hours

Overall mortality within 90 days

Stroke-related and neurological deaths within 90 days

Incidence, severity, and spectrum of all AEs and SAEs

Investigational Medicinal Products

Test Product (Investigational Drug)

Patients randomized to the active arm will receive treatment with 0.9 mg/kg of IV alteplase (maximum 90 mg) per standard stroke dosing.

Comparator

Patients randomized to the placebo arm will receive IV alteplase placebo consisting of 1.7 g of L-arginine, 5 mg of polysorbate 80, and 0.5 g of phosphoric acid.

Non-Investigational Medicinal Products

Comparator

To maintain standard medical care, patients randomized to the IV alteplase placebo arm will receive 325 mg of oral aspirin at the same time that they receive IV alteplase placebo.

Comparator

Patients in the IV alteplase active arm will receive an oral aspirin placebo tablet at the same time they receive IV alteplase. The placebo will be identical in appearance to active aspirin to maintain treatment blinding.

Statistical Methods

Primary Analysis

The primary efficacy analysis will test the hypothesis of superiority of IV alteplase therapy over standard medical care in AIS patients with mild deficits. The primary efficacy outcome is the

Statistical Analysis Plan: Alteplase—Genentech USMA

37/ML29093

5/17/2017

proportion of patients with a favorable outcome, defined by mRS score of 0 or 1 at 90 days post-randomization. The difference in the proportion of mRS 0–1 responders (favorable outcome) at 90 days post-randomization between the IV alteplase arm and the standard medical care arm will be compared via a Cochran-Mantel-Haenszel test, stratified by pre-treatment NIHSS score (0 – 2 vs. 3 – 5), age (< 65 vs. ≥ 65), and last known well time to treatment (0 – 2 hours vs. > 2– 3 hours). The primary efficacy analysis will include all randomized patients, with patients grouped according to the treatment assigned at randomization adhering to the intent-to-treat (ITT) principle. As a sensitivity analysis, results from the univariate Pearson’s chi-square test will also be presented.

Determination of Sample Size

A sample size of 856 is required in order to achieve 80% power for the primary analysis to detect an effect size of 9% absolute difference in the proportion of patients with favorable outcomes between the alteplase and control arms. The above sample size calculation assumes a control proportion of 65% and Type I error probability of 0.025 (one-sided), and uses a group sequential design with one interim analysis for futility (non-binding), based on an O’Brien-Fleming boundary, after 50% of the anticipated sample size have completed the 90-day follow-up assessments. [REDACTED] was used in sample size calculation.

The ITT principle will be applied to the primary analysis and, therefore, to safeguard against dilution of the treatment effect associated with an approximate 5% non-adherence rate (due to lost to follow-up, consent withdrawal, treatment crossovers, and stroke mimics), the above sample needs to be inflated by a factor of 1/0.952 or 1.108 (Friedman et al. 1998). Therefore, a total sample size of 948 is required for this study.

Interim Analysis

One interim analysis of the primary efficacy outcome is planned for clear futility, conducted according to the beta-spending approach (Pampallona et al. 2001) with an O’Brien-Fleming-type boundary. This futility analysis will occur after approximately 50% of patients (or 474) have completed the 90-day assessment.

